1.0 PROTOCOL SUMMARY AND/OR SCHEMA

This is a pilot study of injection of sialyl lewis^a (sLe^a) conjugated to keyhole limpet hemocyanin (KLH) plus the immunological adjuvant QS-21. Eligible patients include those with metastatic

breast cancer who have no evidence of disease or stable disease on hormone therapy. Initially 3 patients will be entered at a lower dose (10 mcg) of sLe^a. If safe, 10 patients will be accrued at the full dose of 30 mcg. If 6 or more of these 10 patients have an immune response at any time point then an additional 10 patients will be accrued and injected with a higher dose of QS-21.

Injections will be administered subcutaneously during weeks 1, 2, 3, 7 and 19. Prior to and during therapy, blood samples will be obtained to assess immune response.

The primary endpoints of this trial are safety and immune response. Clinical response will be monitored but will not be a primary endpoint. A secondary endpoint is the evaluation of blood samples for circulating tumor cells.

2.1 OBJECTIVES AND SCIENTIFIC AIMS

The primary objectives of this trial are to determine the following endpoints after injection with sLe^a-KLH plus QS-21:

- Safety
- The IgG and IgM antibody response to sLe^a and breast cancer cells expressing this antigen

The secondary objective of this trial is to monitor the presence of circulating tumor cells (CTC) prior to, during and after injection with sLe^a-KLH plus QS-21.

Clinical response will be monitored but will not be an endpoint. As part of standard care, patients on this trial will be followed for progression of disease. It is unknown how many patients will enroll with evidence of disease. Therefore, we will report any responses that are observed for these patients in a purely descriptive manner (see section12). This is consistent with the pilot vaccine trials we have previously conducted.

3.0 BACKGROUND AND RATIONALE

3.1 Breast Cancer

Invasive breast cancer is now predicted to affect one in seven American women at some point in their lifetime.¹ A significant number of patient will develop metastatic breast cancer, which in contrast to early stage breast cancer is generally considered incurable.² While patients with AJCC Stage IV breast cancer who have no evidence of disease or stable disease on hormone therapy can live for many years, ultimately their disease will likely become resistant to current treatment options. Additional therapeutic strategies for these patients are needed.

3.2 Treatment Background

[name] and colleagues have shown that some patients have antibodies in their serum which react with highly restricted ganglioside antigens present on melanomas and a variety of other cancers. In some cases, they and others^{3,4} noted that the presence of these antibodies has been associated with an unexpectedly favorable course. As only few patients

have these antibodies in their serum, we are attempting to induce antibody formation by immunizing the patients with tumor vaccines containing the relevant antigens.

Adjuvant immunotherapy of breast cancer with immunizations must be based on the identification of antigens expressed by breast cancers, which are immunogenic. While many antigens have been identified on breast cancers using murine monoclonal antibodies, very few of these are known to be recognized by the human immune system. Several of the antigens commonly identified on breast cancer cells include the gangliosides GM2 and Globo H⁵, blood group-related antigens TF, sTn, Lewis y (Le^y)⁶ and the protein MUC1⁷.

3.2.1 Keyhole Limpet Hemocyanin (KLH) Various methods have been used to increase the immunogenicity of antigens, in particular to induce an IgG response. The approach that [name] and colleagues have found to be most successful at inducing an IgG response against the closely related T antigen in the mouse has been covalent attachment to keyhole limpet hemocyanin (KLH). KLH is an immunogenic protein which is derived from the blood of the keyhole limpet. This approach also resulted in anti-T antigen delayed type hypersensitivity reactions and partial protection against cancer cells expressing T antigen.⁸ Studies of immunological tolerance and of ways to overcome it have shown that in a variety of experimental systems, T-cell (not related to T antigen) unresponsiveness is more rapidly induced and more easily maintained than B cell unresponsiveness.⁹ Levels of circulating antigens suitable for maintaining T-cell tolerance frequently fail to maintain B cell tolerance. Consequently if T-cell help is provided (as by potent irrelevant antigens such as KLH covalently attached to the desired immunogen), antibodies can be induced to tolerated T-cell dependent antigens. This approach has been successfully used to induce IgG antibodies against a variety of carbohydrate antigens, and the titer of antibody induced is greatly augmented with the use of immunological adjuvants.¹⁰

3.2.1.1 Conjugation of antigens to KLH can be accomplished using a direct method or with a bifunctional linker MMCCH (M2C2H): (4-(4-N-maleimidomethyl) cyclohexane-1-carboxyl hydrazide. This latter method of conjugation was developed to improve the antigen epitope:KLH ratio.¹¹ In mice, this method of conjugation resulted in higher antibody titers following immunization with an sTn based vaccine. This method of conjugation has also been evaluated at MSKCC with the Globo H-KLH plus QS-21 construct in breast cancer patients (protocol 97-86).

3.2.2 Immune Adjuvants

QS-21 In addition to KLH, the immunological adjuvant QS-21 has also been used to increase immunogenicity of various antigens. QS-21 is a saponin fraction from the bark of the South American tree Quillaja saponaria Molina.¹² Immunization of mice with synthetic MUC1 peptides conjugated to KLH and mixed with QS-21 resulted in significant antibody titers against MUC1 peptide and MUC1 positive tumor cells in comparison with minimal immune response to unconjugated MUC1 peptides mixed with BCG or QS-21.¹³ Groups of melanoma patients have been immunized with various constructs containing the adjuvants DETOX, BCG and QS21 or no adjuvant at all. QS-21 was a significantly more effective adjuvant than the others, producing significantly higher titer IgM and IgG antibodies.¹⁴ A dose of 100 mcg of QS-21 was found to be minimally toxic and immunogenic.¹⁵ Therefore, QS-21 was selected for

future trials due to its adjuvanticity and lack of toxicity. It has also proven nontoxic and highly effective at augmenting the immunogenicity of an FeLV subunit vaccine in cats¹⁶ and an HIV-1 recombinant vaccine in Rhesus monkeys.

3.3 MSKCC Experience with Immunization of Breast Cancer Patients

Immunization against antigens found on tumor cells represents a potential therapeutic strategy for breast cancer patients. We have conducted several clinical trials at MSKCC in high risk breast cancer patients to assess the safety and immunogenicity of various single antigens conjugated to keyhole limpet hemocyanin (KLH) and mixed with the immune adjuvant QS21. Antigens included the peptide MUC-1 and the carbohydrates Globo-H, GM2 and STn[clustered] (protocol numbers 94-130, 95-67, 97-123, 99-023). These immunizations were well-tolerated with the most common toxicities including transient local skin reactions at the injection site and mild flu-like symptoms. Although, there were no definite autoimmune reactions attributable to the injection, several patients developed hypothyroidism or hyperthyroidism. The majority of patients developed IgM and IgG antibody titers reactive with the immunizing antigen. There were no significant differences in the immune response observed among patients with no evidence of disease or those with stable disease. No definite T cell responses were elicited in the MUC-1 trials.¹⁷⁻²⁰

We subsequently evaluated patients on protocol 01-019 with a polyvalent construct containing 7 antigens conjugated to KLH and mixed with either QS21 or GPI-0100 (a semi-synthetic saponin).²¹⁻²³ The injections were well tolerated with common local skin reactions and mild flu-like symptoms. Several patients receiving GPI-0100 developed a transient Grade 1-3 elevation in the hepatic enzymes (AST, ALT). Following an extensive hepatic evaluation, it was felt that the GPI-0100 was the likely source of the hepatotoxicity. Therefore, the adjuvant GPI-0100 will not be incorporated into the current breast cancer trial. The majority of patients also developed antibody titers reactive with multiple immunizing antigens.

3.4 Rationale for Evaluation of sialyl Lewis^a (sLe^a)-KLH plus QS-21

The carbohydrate antigen sLe^a is the antigen recognized by monoclonal antibody 19.9 and is commonly expressed on breast cancer cells. In a study of 43 breast cancer patients with infiltrating ductal carcinoma it was found in about 79% of samples.²⁴ There was high expression in patients with greater node involvement. sLe^a may be a ligand for endothelial leukocyte adhesion molecule and therefore have an impact on metastatic potential.

sLe^a is expressed primarily as a glycolipid on the surface of cancer cells. We are preparing a polyvalent vaccine for evaluation in patients with breast cancer. It contains four antigens expressed on mucins (MUC1, Tn, sTn and TF) and three antigens expressed as glycolipids (GM2, globo H and Lewis Y). There are advantages to glycolipid antigens including greater susceptibility to activation of complement in the presence of antibodies and greater induction of complement mediated cytotoxicity, as recently described.^{24a} We have recently learned that Lewis Y is poorly immunogenic, inducing antibodies in fewer than 30% of vaccinated patients. If sLe^a proves immunogenic in this trial, we plan to replace Lewis Y in the polyvalent construct with sLe^a.

In this protocol, we propose to evaluate a construct containing the antigen sLe^a for toxicity and immunogenicity. If the injections are well tolerated and immunogenic, then sLe^a will be incorporated into a future polyvalent construct. This is the first time that sLe^a is being evaluated in humans.

Our prior breast cancer immunization protocols used 100 mcg of QS-21. The greatest toxicity primarily occurred during weeks 2 and 3. In an attempt to increase the immunogenicity of the construct, if six or more of the initial ten patients demonstrate an immune response against sLe^a and the injection is well tolerated, the dose of QS-21 will be increased to 150 mcg during weeks 1, 7 and 19 in a second group of 10 patients. We do not anticipate significant increases in toxicity as prior evaluations of 200 mcg of QS-21 were tolerated.

The potential benefits of this study include generation of an anti-tumor response by stimulation of the immune system. While it is possible that this treatment will result in shrinkage of breast cancer tumors, delay a recurrence or decrease the risk of progression, it is not known whether these effects will occur. If this study demonstrates that the sLe^a-KLH conjugate is safe and immunogenic, it will be incorporated into a polyvalent vaccine that will be evaluated in high risk breast cancer patients for clinical benefit.

3.5 Evaluation of Circulating Tumor Cells (CTC)

Circulating tumor cells (CTC) can be detected in the blood from patients with various primary or metastatic carcinomas.²⁵⁻²⁹ Recently the development of immunomagnetic separation strategies has increased the sensitivity of these assays.^{28,29} Several studies have reported that the presence of CTC predicted shortened disease free and overall survival times. These studies demonstrate that detection of CTC correlates with prognosis at baseline and that changes in CTC levels during and after treatment may be more predictive than other measures.³⁰⁻³⁴ Monoclonal antibody based therapy (trastuzumab) with or without additional chemotherapy was particularly effective at eliminating CTC. This was associated with improved disease free and overall survival.²⁸

Use of peripheral blood immunomagnetically enriched for tumor cells using labeled antibodies targeting epithelial cell surface markers on breast cancer cells and quantitated using a CellSpotterAnalyzer is now FDA approved for this purpose in breast cancer patients. Veridex, LLC. has provided MSKCC with a CellSpotterAnalyzer for this purpose in patients with prostate and breast cancer. To date, [name], Chief of the MSKCC Department of Clinical Laboratories, has validated the assay in prostate cancer patient using the same labeled antibodies which are FDA approved for use in breast cancer patients.

Two studies have identified CTC in approximately 95% of breast cancer patients with Stage I/II disease prior to surgery.^{35,26} After resection of all known disease, 30% of patients continued to have CTC that persisted for at least 2 weeks. The patients that we propose to evaluate are patients at a high risk for recurrence. We estimate that at least 30% of these patients will have demonstrable CTC.

In this study, CTC will be evaluated in an exploratory manner to determine whether they can be detected in this patient population at baseline and if so whether there is evidence

of a decline in those patients who have an immune response. CTC will be monitored prior to, during and after injection with sLe^a-KLH plus QS-21. The patient and their primary oncologist will be notified of all CTC results. These results will be used for research purposes and will not be used during the study to alter clinical care. Although some physicians at other centers may use CTC results to evaluate response to therapy, this is not considered standard care at MSKCC.

4.1 OVERVIEW OF STUDY DESIGN/INTERVENTION

4.2 Design

This is a pilot study designed to assess the safety and immunogenicity of a sLe^a-KLH plus QS-21 construct in patients with metastatic breast cancer. Initially 3 patients will be accrued to the study at a 10 mcg dose of sLe^a. If safe, then 10 patients will be accrued at the 30 mcg dose of sLe^a. If 6 or more of these 10 patients have an immune response at any time point then an additional 10 patients will be accrued and injected with a higher dose of QS-21. Toxicities will be monitored during the study. Patients will be instructed to complete a patient diary and document any side effects.

Patient blood samples will be evaluated for an IgG and IgM antibody response to sLe^a and breast cancer cells expressing this antigen. Immunological response for a patient is defined as an antibody response of greater than 1:80 if baseline value was 0 and at least an increase of 8-fold if baseline value is greater than 0. Patient blood samples will also be monitored for the presence of circulating tumor cells pre study and then during weeks 5, 13, and 23.

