10.0 EVALUATION DURING TREATMENT/INTERVENTION

The study evaluation will include parameters to assess the safety of the injections as well as assessments of immunity to sLe^a (Appendix A). Interval safety assessments will include the „Patient Diary“ (Appendix B). Patients will be provided with Appendix A and B. Long term followup will also be maintained to assess toxicity. Although not a primary endpoint, patients will be monitored for any evidence of an anti-tumor effect. Imaging to assess extent of disease will be performed at baseline, then as appropriate for clinical circumstances. Patients with metastatic disease are often evaluated with imaging every 3 months as standard of care. Clinical benefit will also be assessed by physical examination and biochemical studies as outlined below.

SUMMARY TABLE OF EVALUATION

STUDY WEEK VACCINATION	Pre	1	2	3	5	7	9	13	19	23	q3 months ^g
Clinical:											
History	X	X				X		X	X	X	X
Physical Exam	X	X				X		X	X	X	X
CBC w/ Diff	X					X		X	X		
COMP ^b	X				X	X		X	X	X	
CEA, CA153	X										X ^f
TSH	X						X				X
Urinalysis	X										
Pathology Review	X										
Pregnancy Test	X ^a										
Rectal/Hemoccult	X										
Imaging:											
Bone scan	X									X ^f	
CT Scans	X									X ^f	
Response Assessments ^d									X ^f	X ^f	
Anti-sLe ^a											
Immunity:											
Serology (3 RTT)	X	X ^e	X ^e	X ^e	X	X ^e	X	X	X ^e	X	X
CTC Assay	X				X		X		X		X

^a Within 2 weeks of the first injection for a premenopausal patient..

^b Includes total bilirubin, AST, ALT, Sodium, Potassium, Chloride, CO₂, Calcium, Glucose, Total Protein, Albumin, Alkaline Phosphatase, Creatinine, BUN, Bilirubin.

^c Patients may be asked to obtain tissue blocks from previous diagnostic/therapeutic procedures.

^d Overall response assessment includes the measurement of tumor by non-imaging studies such as physical exam.

^e Blood must be drawn before administration of vaccine at week 1,2, 3, 7 and 19. An extra 100ml of heparinized blood may be drawn once (during weeks 9-23) during the course of immunizations depending on the serologic response in individual patients, at the principal investigators discretion, for evaluation of the immune response at the clonal level by hybridoma production.

^f These studies will be performed as standard of care if deemed appropriate by the patient's physician.

^g If feasible, a history and physical examination and serology will be obtained every 3 months until evidence of disease progression.

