10.1 Clinical Course

Patients will be examined by oncologists at Memorial Hospital and have laboratory and radiographic studies performed as outlined in the above table. As this is a pilot study primarily concerned with effect of injection of sLe^a on immune response, intensive clinical follow-up at Memorial Hospital will not be required. However, if feasible, patients who remain clinically stable will be asked to return to Memorial Hospital every 3 months for a history and physical examination and laboratory studies.

The patient and their primary oncologist will be notified of all CTC results. These results are for research purposes and will not be used during the study to alter clinical care.

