10.2 Immunologic Response

Serological response: Three 10 ml red top tubes will be drawn before the first injection, before each subsequent injection and also during weeks 5, 9, 13 and 23. Sera will be evaluated for reactivity against sLe^a in ELISA and/or immunoprecipitation-western blot assays. These assays detect antibodies against sLe^a and confirm identity of the reaction. If serologic reactivity is detected, then additional blood (~10ml) may be drawn at later times after the injections are completed to determine the duration of this response (every 3 months if feasible). An extra 100ml of heparinized blood may be obtained once during the course of immunizations depending on the serologic response in individual patients at the principal investigators discretion, for hybridoma production. This will be used for evaluation of the B-cell response to vaccination at the clonal level by establishment of monoclonal antibodies. This will be performed in collaboration with MabVax Therapeutics, Inc., (San Diego, CA). It will make possible more detailed analysis of the most immunogenic epitopes on sLe^a and more detailed comparison of the avidity of the induced IgG and IgM antibodies than is possible with sera.

T cell response will not be evaluated since this is a carbohydrate antigen and significant T cell response is not anticipated. The immune response analyses will be conducted in the laboratory of [name] under [name] supervision.

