11.0 TOXICITIES/SIDE EFFECTS

In our earlier breast cancer immunization trials, common toxicities included local skin reactions at the injection sites, flu-like symptoms (ie, fever, fatigue, myalgias, arthralgias), and less frequent symptoms such as pruritis, rashes, diarrhea, nausea and vomiting. These symptoms were transient and usually of less than 5 days duration. In addition, minimal transient decreases in hematologic values, primarily white blood cell counts and lymphocyte counts were noted. It is unlikely that these fluctuations were due to the vaccine. Transient elevation in various laboratory values (ie glucose, liver enzymes) were observed and also thought unrelated to the vaccine.

Since the antigen in this injection is present on the surface of normal tissues, the theoretical possibility of a serious autoimmune reaction exists. In our previous breast cancer trials, there was no consistent evidence of an autoimmune reaction due to the immunization. Several episodes of hyperthyroidism or hypothyroidism have occurred on these trials. Patients were subsequently treated with radioactive I-131 or thyroid supplementation. It is unclear whether these events were related to the immunization. Therefore, the thyroid stimulating hormone level will be monitored pre therapy, during therapy and post therapy.

In addition, no definite evidence of autoimmunity has been observed in immunization trials in prostate or ovarian cancer at MSKCC (personal communication with [name] and [name]). Autoimmune reactions may be controlled by cessation of the immunization and anti-inflammatory medications. The symptoms would be dependent on the organs involved. These may include but are not limited to diarrhea, dyspnea, numbness, weakness, vaginal bleeding, inflammation of the breast or pancreas and blood in the stool. This autoimmunity is considered unlikely however, since cytotoxic T-cells and antibodies against various antigens found on breast cancer cells have been recognized in the peripheral blood of patients with breast cancer in the absence of any evidence for autoimmunity. Some patients have also demonstrated baseline antibody titers against various antigens used in our prior trials.

In MSKCC protocol 01-019 several episodes of transient asymptomatic elevation of the AST and ALT levels (grade 1-3) were observed. The finding was thought to be due to the GPI-0100 and we do not anticipate this toxicity on this trial using QS-21.

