12.1 Long Term Followup

Patients will be followed every 3 months if feasible following completion of the vaccine trial, until evidence of disease progression. Shorter time intervals between visits may be required, according to the standard of care for the patient's state of disease.

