12.3 Clinical Response

Patients will be monitored for anti-tumor effect, although this is not a primary endpoint. Patients who have evidence of disease will be evaluated at week 19 or at the discretion of their physician. Responses will be categorized using RECIST response criteria as follows:

Complete Response (CR):

Target Response Criteria: The disappearance of all known disease and no new sites or disease related symptoms confirmed at least 4 weeks after initial documentation. All sites must be assessed, including non-measurable sites, such as effusions, or markers

Non-Target Response Criteria: Disappearance of all non-target lesions and normalization of tumor markers level confirmed at least 4 weeks after initial documentation.

Partial Response (PR):

Target Response Criteria: At least a 30% decrease in the sum of the longest diameters of target lesions, taking as a reference the baseline sum of the longest diameters confirmed at least 4 weeks after initial documentation. PR is also recorded when all measurable disease has completely disappeared, but a non-measurable component (i.e., ascites) is still present but not progressing.

Stable Disease (SD):

Target Response Criteria: Neither sufficient shrinkage to qualify for partial response nor sufficient increase to qualify for progressive disease.

Non-Target Response Criteria: Persistence of one or more non-target lesions and/or the maintenance of tumor marker level above the normal limits.

Progressive Disease (PD):

Target Response Criteria: At least a 20% increase in the sum of the longest diameters of target lesions, taking as reference the smallest sum of the longest diameters recorded since the treatment started; or the appearance of one or more new lesions; or the unequivocal progression of a non-target lesion.

Non-Target Response Criteria: Appearance of one or more non-target lesions and/or unequivocal progression of existing non-target lesions.

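### Section 4.2 and the Section 10 table give different CTC sampling weeks, and the table as read has no fixed CTC sample after the week of the last injection

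*Combined protocol and SAP*

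**What the plan says.** Section 4.2 (Design) sets the CTC samples in one sentence: "circulating tumor cells pre study and then during weeks 5, 13, and 23". That is four time points, with no 3-monthly sample.

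The summary table in Section 10.0 has 11 columns: Pre, weeks 1, 2, 3, 5, 7, 9, 13, 19 and 23, and q3 months. In the text copy, the CTC row is marked at Pre, weeks 5, 9 and 19, and q3 months. Weeks 13 and 23 are blank.

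Three places describe the 3-monthly visit:
- Footnote g, attached to the q3-month column: "If feasible, a history and physical examination and serology will be obtained every 3 months until evidence of disease progression". It does not list CTC.
- Section 10.1: "if feasible, patients who remain clinically stable will be asked to return to Memorial Hospital every 3 months".
- Section 12.1: "Patients will be followed every 3 months if feasible following completion of the vaccine trial, until evidence of disease progression".

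Section 4.3 places the five injections in weeks 1, 2, 3, 7 and 19. Sections 2.1 and 3.5 commit the trial to measuring CTC before, during and after injection. Section 14.0 plans an exploratory look at whether CTC are detectable at baseline and, if so, whether they decline in immune responders. Section 8.1 covers only the baseline CTC draw. No other section gives CTC weeks after baseline.

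**The concern.** Site staff usually work from the evaluation table and analysts from the design text. Here the two lead to different data. One yields samples at weeks 13 and 23, the other at weeks 9 and 19, and a sample not drawn cannot be recovered.

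The more serious consequence is at the end of the course. If the table is followed as it reads, no fixed CTC sample falls later than the week of the fifth injection. What is known about CTC after the full course would come only from 3-monthly visits, which clinically stable patients are asked to make if feasible and which end at progression. Section 3.5 itself says that CTC levels track prognosis. A decline seen among those who return could therefore partly reflect who returned. CTC is the only secondary objective, so the inconsistency bears on all of it.

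**Working it through.** There is no sample-size or error-rate figure to reproduce. The check sets the two schedules side by side against the injection weeks (1, 2, 3, 7, 19; Section 4.3).

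**1. Time points**

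| | Pre | 5 | 9 | 13 | 19 | 23 | q3 months |
|---|---|---|---|---|---|---|---|
| Section 4.2 | X | X | | X | | X | |
| Section 10 table, as read | X | X | X | | X | | X |

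Section 4.2 names 4 time points and the table marks 5. They share 2 (Pre and week 5).

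**2. Position relative to the injections**

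| Source | Week | Injections in earlier weeks | Weeks since the latest of them |
|---|---|---|---|
| Both | 5 | 3 | 5 − 3 = 2 |
| Section 4.2 | 13 | 4 | 13 − 7 = 6 |
| Section 4.2 | 23 | 5 | 23 − 19 = 4 |
| Table | 9 | 4 | 9 − 7 = 2 |
| Table | 19 | 4 | 19 − 7 = 12 (week of injection 5) |

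The order of draw and injection in week 19 is not stated for CTC. Footnote e says "Blood must be drawn before administration of vaccine at week 1,2, 3, 7 and 19", but its marker is on the serology row. If it also covers CTC, the week-19 sample follows only four of the five injections.

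**3. Fixed samples later than the week of injection 5**

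Planned patients are 3 + 10 = 13 without the second group and 3 + 10 + 10 = 23 with it. If all complete:
- Section 4.2: one each (week 23), so 13 to 23 samples.
- Table: 0.

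**4. First conditional sample under the table**

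The starting point for the 3-monthly visits is not given. Taking 3 months as 13 weeks and counting from week 19 or week 23:
- 19 + 13 = week 32, which is 13 weeks after the last injection.
- 23 + 13 = week 36, which is 17 weeks after it.

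Section 4.2 gives 4 weeks.

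**5. Could the table row simply be misaligned?**

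Moving the marks at weeks 9 and 19 one column to the right gives weeks 13 and 23, so this has to be considered.
- The CTC row has exactly 11 cells. A shift would require one blank lost before week 13 and another gained before q3 months.
- The response-assessment row is marked at weeks 19 and 23, consistent with Section 12.3: "Patients who have evidence of disease will be evaluated at week 19 or at the discretion of their physician".
- The TSH row is marked at Pre, week 9 and q3 months, consistent with Section 11.0: "the thyroid stimulating hormone level will be monitored pre therapy, during therapy and post therapy".
- The serology row carries its footnote marker at weeks 1, 2, 3, 7 and 19, as footnote e lists. That row is full, so it confirms only the column order.

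These checks make a shift of the whole table unlikely. They do not exclude a shift in the CTC row alone. If that happened, weeks 5, 13 and 23 would agree with Section 4.2, but the q3-month mark would still have no counterpart there.

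**The case against.** The strongest reply is that the main consequence rests on one row of a table that is visibly damaged in the text copy: two header labels are merged, a row label is split, and footnote c has no marker. The alignment checks are also modest. An 11-cell count would appear in any fixed grid, TSH at week 13 would fit its text as well as week 9, and the other rows vouch only for themselves. This stands, and it is why the original page must be checked before the table is changed. It does not remove the q3-month mismatch, which survives a shift.

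Second, Section 13.1 lets a patient with progression stay on study if the primary physician agrees and only hormone therapy changes. That is true, but the 3-monthly visit remains tied to feasibility and clinical stability and ends at progression. Applying footnote g to CTC is an inference from the column heading. If it does not apply, the 3-monthly CTC draw is specified even less firmly.

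Third, the CTC analysis is exploratory. No test or decision depends on it, and the results do not alter care during the study. The count of 13 to 23 also includes every patient, whereas the decline question concerns immune responders with CTC at baseline. At the 30% that Section 3.5 gives as a minimum, that is 0.30 × 13 = 3.9 or 0.30 × 23 = 6.9 patients, before restricting to responders. This limits the weight of the point. It also means that few informative patients are available, so losing their post-course samples matters for this objective.

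**Conclusion.** The concern holds. The design text and the evaluation table, as it reads, agree on only baseline and week 5, and no other section resolves the difference. Under the table there are 0 fixed CTC samples after the week of the last injection, against 13 to 23 under Section 4.2 if all patients complete. The first later sample would come about 13 or 17 weeks after the last injection instead of 4, and only from patients who meet the conditions for the 3-monthly visit.

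This rests on the column positions in the text copy and, for the 13 or 17 weeks, on the assumed start of the 3-monthly visits. If the original page shows weeks 13 and 23, the point about a missing fixed sample falls away and only the unexplained 3-monthly CTC mark remains. The effect is confined to the secondary objective. It should be corrected, but it does not threaten the trial's main conclusions.

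**What to change.** 1. Check the CTC row of the Section 10 table on the original page.
2. If the marks are at weeks 9 and 19, reconcile the table and Section 4.2 to one schedule that keeps a fixed sample after the last injection. The simplest way is to move the two marks to weeks 13 and 23, as Section 4.2 already states.
3. In either case, say in Section 4.2 whether the 3-monthly CTC sample is planned.

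The cost is two marks in one table row and a few words of text. Serology is already drawn "before each subsequent injection and also during weeks 5, 9, 13 and 23" (Section 10.2), so no visit is added, and the number of on-study CTC draws after baseline stays at three. Keeping weeks 9 and 19 and adding week 23 would instead cost one more assay per patient, 13 to 23 in all.
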